4. OVERALL STUDY DESIGN AND PLAN

This study was a multicenter and open-label study evaluating the real-world use of 0.07 mg lorecivint (LOR) injected into one or both knee joints of subjects with OA at Day 1. Additional injections were to be performed per the OA treatment algorithm available in the study protocol.

The sponsor elected to terminate this study early for business reasons. All active subjects were requested to complete an early termination (ET) visit. Subjects who were recently injected were requested to participate in an ET visit 30 days (+14 days) after their last injection. Subjects on study more than 30 days since their last injection, were requested to participate in an ET visit as soon as possible. During the ET visit, only safety data were to be collected.

2.1 Selection of Study Population

The study population included ambulatory males and females between 40 and 80 years of age, inclusive, with knee OA. Complete inclusion/exclusion criteria are available in the study protocol.

2.2 Method of Treatment Assignment and Randomization

This was an open-label study.

2.3 Treatment Blinding

This was an open-label study.

2.4 Minimization of Missing Data

2.4.1 Collection of Clinical Outcomes

As part of the real-world setting design, the clinical outcomes data were collected on paper at each applicable study visits. Upon completion of each assessment and questionnaire, the subjects were to sign or initial, then date the source documents to indicate that they were reported accurately.

2.4.2 Rescue Medication

Not applicable to this study (see protocol section 7.8).

2.4.3 Prohibited Medications, Treatments, and Procedures

During the conduct of the study, certain medications, treatments, and procedures were prohibited (see protocol section 7.6). The overall intent of these prohibitions was to minimize any possible bias in the assessment of the clinical trial endpoints. However, the protocol did allow for the use of these prohibited therapies if and only if they were required to ensure subject safety.

Investigators were instructed to notify the sponsor's Medical Monitor, who would note the prohibited therapy as a protocol deviation. These deviations were categorized as major or minor depending on the nature and timing of the interventions. Subjects were not automatically discontinued based upon prohibited therapy use, allowing for continued data collection and assessment of the impact of prohibited therapy on key endpoint data.

2.4.4 Intermittent Missing Data

Ongoing programmatic surveillance of eCRFs and visit compliance using intranet dashboards during trial conduct led to the identification of subjects that were not compliant with protocol. Sites were notified of possible non-compliant subjects and were instructed to address any possible technical or conduct issues with these subjects prior to key endpoint data collection times. The ongoing monitoring of eCRFs was a specific strategy designed to minimize the loss of key endpoint data.

3. SAMPLE SIZE DETERMINATION

The originally-planned sample size was not based on statistical considerations. A sample size of 300 subjects was a reasonable sample size to observe patterns of use of LOR and other IA injections.

4. ANALYSIS POPULATIONS

4.1 Full Analysis Set

The Full Analysis Set (FAS) includes all subjects who receive a study injection.

4.2 Safety Analysis Set

The Safety Analysis Set (SAS) includes all subjects who receive a study injection. In this study, FAS and SAS will be identical.

5. GENERAL ISSUES FOR STATISTICAL ANALYSIS

5.1 General Statistical Methodology

Efficacy analyses will not be performed as the sponsor elected to terminate this study early; subject-level listings will be provided for all efficacy assessments. General safety analyses will be performed on the SAS. The number of evaluable subjects may vary by endpoint/timepoint based on missing data.

For continuous variables, the outcome measure at each visit, as well as the absolute change (outcome at visit – outcome at baseline), will be summarized using descriptive statistics (number of subjects, mean, SD, median, minimum, and maximum). Categorical variables will be summarized with counts and percentages.

Data collected from unscheduled visits will not be included in summary tables but will be included in subject-level listings as appropriate.

5.1.1 Baseline

Baseline is defined as the last value recorded for any given parameter prior to the first study medication injection.

5.1.2 Data Handling for Patients Who Withdrew from the Study

If a subject discontinues the study, early termination assessments were to be performed according to the protocol. If these assessments occurred during a scheduled visit, they will be associated with that visit for the purposes of SAS analysis. The sponsor elected to terminate this study early. All active subjects were requested to complete an early termination (ET) visit. Subjects who were recently injected were requested to participate in an ET visit 30 days (+14 days) after their last injection. Subjects on study more than 30 days since their last injection, were requested to participate in an ET visit as soon as possible. During the ET visit, only safety data would be collected.

5.2 Interim Analysis

Not applicable.

5.3 Efficacy Assessments

5.3.1 Pain NRS

The Pain NRS is an 11-point scale [0-10] for subject self-reporting of average knee pain in the previous 24 hours, where 0 represents no pain and 10 represents extreme pain. The pain NRS was to be completed by the subject for both knees at Day 1, Months 3, 12, 24, and 36 (EOS)/ET, and at each Unscheduled Injection Visit and 3-Month Post-Injection Follow-Up Visit.

5.3.2 WOMAC

The WOMAC is a widely used, proprietary outcome measurement tool used by health professionals to evaluate the condition of patients with OA of the knee and hip, including pain, stiffness, and physical functioning of a target joint. The WOMAC Version NRS 3.1 was to be completed by the subject for both knees at Day 1, Months 3, 12, 24, and 36 (EOS)/ET, and at each Unscheduled Injection Visit and 3-Month Post-Injection Follow-Up Visit.

WOMAC consists of 24 questions in three domains: physical function (17 questions), pain (5 questions) and stiffness (2 questions). If one pain, one stiffness, or 1-3 physical function items are missing, the average value for the subscale will be used as the missing item value(s). The response for each question in the NRS format ranges from 0 to 10. Each domain subscore as well as a total score are calculated by adding together the numerical responses for a range of 0 to 240 total points. If two or more pain, both stiffness, or four or more physical function items are missing, the subject's WOMAC is regarded as invalid, and the subscale(s) or total will not be computed (Bellamy, WOMAC Osteoarthritis Index User Guide XI, 2015). For the listing, WOMAC scores will be linearly transformed to a 0-100 scale, where 0 represents no difficulty and 100 represents extreme difficulty.

5.3.3 Knee Injury and Osteoarthritis Outcome Score (KOOS)

The KOOS Assessment is used to assess a subject's opinion about their knee and associated problems. Subjects will complete the KOOS subscales for Symptoms, Function (Sports), and knee-related Quality of Life. The KOOS was to be completed by the subject for both knees at Day 1, Months 3, 12, 24, and 36 (EOS)/ET, and at each Unscheduled Injection Visit and 3-Month Post-Injection Follow-Up Visit.

5.3.4 12-Item Short Form Health Survey (SF-12)

The SF-12 is a widely used questionnaire that relies upon subject self-reporting to measure the subject's health-related quality of life. The SF-12 was to be completed by the subject at Day 1, Months 3, 12, 24, and 36 (EOS)/ET.

5.3.5 Work Productivity and Activity Impairment (WPAI) Questionnaire

The WPAI questionnaire is a validated instrument to assess the impact of disease on paid work and activities. The WPAI was to be completed by the subject at Day 1, Months 3, 12, 24, and 36 (EOS)/ET.

5.3.6 Patient Acceptable Symptom State (PASS) Questionnaire

The PASS questionnaire was used to ask subjects the following using a paper questionnaire: "Taking into account all the activities you have during your daily life, your level of pain, and also your functional impairment, do you consider that your current state is satisfactory?" Subjects were able to choose the answers of "Yes" or "No.". The PASS was to be completed by the subject at Day 1, Months 3, 12, 24, and 36 (EOS)/ET.

5.3.7 40-meter Walk Test

At a subset of sites, the 40-meter walk test was to be administered. The 40-meter walk test was a performance-based measure used to assess walking speed over the distance of 40 meters. The 40-

meter walk was to be completed by the subject at Day 1, Months 3, 12, 24, and 36 (EOS)/ET, and at each Unscheduled Injection Visit and 3-Month Post-Injection Follow-Up Visit.

5.3.8 Timed Up and Go (TUG) Test

At a subset of sites, TUG test was to be administered. The TUG test is a performance-based measure of mobility, balance, walking ability, and fall risk. The TUG test was to be completed by the subject at Day 1, Months 3, 12, 24, and 36 (EOS)/ET, and at each Unscheduled Injection Visit and 3-Month Post-Injection Follow-Up Visit.

5.4 Safety Assessments

5.4.1 Adverse Events

An AE is any unfavorable and unintended sign, symptom, or disease temporally associated with the use of an IP or other protocol-imposed intervention, regardless of attribution. Signs and symptoms of exacerbation or worsening of knee OA were captured in the context of efficacy assessments. Anticipated fluctuations or anticipated deterioration (in the opinion of the Investigator) of the underlying disease (knee OA) were not considered as AEs.

Severity was assessed utilizing the CDISC AESEV, which classifies AEs as mild, moderate, or severe. For analysis, relationship will be dichotomized into Unrelated (combining Not Related and Unlikely Related) and Related (combining Possibly Related and Probably Related).

5.4.2 Vital Signs and Weight

Vital signs were measured by a qualified staff member at all in-person visits. At each time point, the following vitals were measured:

- Body temperature
- Pulse rate
- Blood pressure (systolic and diastolic)

Any measurement that was, in the opinion of the Investigator, abnormal AND clinically significant was considered as an AE if found after the Day 1 study medication injection(s).

Weight measurements were to be taken at the Screening Visit and at Months 12, 24 and 36 (EOS) or ET.

5.4.3 Clinical Laboratory Evaluations

Fasting specimens for clinical laboratory analysis were to be collected at Screening Visit and Months 12, 24, and 36 (EOS) or ET. At a minimum, the following tests were conducted:

- **Chemistry panel:** Albumin, alkaline phosphatase (ALP), alanine aminotransferase (ALT), aspartate aminotransferase (AST), blood urea nitrogen, bicarbonate, calcium, calcium (corrected total), chloride, creatinine, glucose, lactate dehydrogenase (LDH), potassium, sodium, bilirubin (total), and uric acid
- **Hematology:** Hemoglobin, hematocrit, red blood cell (RBC) count, white blood cell (WBC) count with differential, and platelet count

- **Urinalysis:** Clarity, specific gravity, pH, protein, glucose, ketones, nitrite, leukocyte esterase, and occult blood

Urine microscopy was to be performed if urinalysis urine protein, leukocyte esterase, occult blood, or nitrite values were out of range, or if the Investigator deemed that the microscopy was clinically warranted.

6. STUDY SUBJECTS AND DEMOGRAPHICS

6.1 Disposition of Subjects and Withdrawals

Subject disposition will be presented in a summary table detailing the number and percentage of subjects who were consented, treated, or discontinued (e.g. adverse event, subject decision, etc.) overall. As the sponsor terminated the study, no subjects were considered to have completed. Subject disposition for treated subjects will be presented by study site. An additional table will be prepared to summarize the number of subjects included in the analysis sets. The disposition for individual subjects will be listed along with additional information on discontinued and screen failed subjects.

6.2 Protocol Deviations

A protocol deviation is defined as any noncompliance with the clinical trial protocol requirements. The noncompliance may be either on the part of the subject, the Investigator, or the study site staff.

Deviations are summarized into one of the following categories:

- Informed Consent Form
- Enrollment
- Procedures
- Labs/Specimens
- Study Visits
- Investigational Product
- Subject Non-Compliance
- Serious Adverse Events

Deviations are categorized as major or minor by a cross-functional team according to pre-defined criteria established in the Protocol Deviation Classification Guideline.

- A major deviation is defined as a divergence from the protocol that materially (a) reduces the quality or completeness of efficacy data, (b) makes the informed consent inaccurate, or (c) impacts a subject's safety, rights or welfare.
- A minor deviation is defined as a divergence from the protocol that deviates from the procedures and guidelines outlined in the protocol, but is not classified as a major deviation (i.e. the deviation does not materially (a) reduce the quality or completeness of the data, (b) make the informed consent inaccurate, or (c) impact a subject's safety, rights or welfare).

Major protocol deviations will be summarized by site and category, and all protocol deviations will be listed for each subject. Additionally, the COVID-19 pandemic related protocol deviations will be summarized separately.

6.3 Demographics and Other Baseline Characteristics

Demographic and baseline characteristics, including sex, race, ethnicity, age at consent, weight, height, body mass index (BMI), Kellgren-Lawrence (KL) grade for each knee, Widespread Pain Index (WPI), Symptom Severity Question 2 (SSQ2), investigator-assessed OA laterality, LOR treatment on Day 1, and primary insurance coverage will be presented overall. Continuous variables will be summarized with descriptive statistics and categorical variables will be summarized with frequencies and percentages. The summaries will be provided for the safety analysis set. Subject level listings of above parameters and a separate listing containing the individual responses for the Charlson Comorbidity Index will also be provided.

6.4 Medical History

A summary of reported medical history will be provided by MedDRA system organ class on the Safety Analysis Set. A subject-level listing will provide further information on each event.

7. EFFICACY ANALYSIS

Efficacy analyses will not be performed as the sponsor elected to terminate this study early. Subject-level listings will be provided for all efficacy assessments.

7.1 Estimands

Not applicable for this study.

8. SAFETY AND TOLERABILITY ANALYSIS

The analysis of safety outcome measures will be performed on the Safety Analysis Set. No formal statistical tests are planned for safety.

8.1 Adverse Events

All AEs collected in this study are treatment emergent events that occur during the course of the study that are not present prior to Day 1 study medication injection, or, if present at the time of study medication injection, have worsened in severity during the course of the study.

Since the study was terminated early, and only 2 adverse events were reported, tables will not be generated. Only subject-level listings will be provided.

8.2 Clinical Laboratory Evaluations

Since the study was terminated early, no subjects completed a post baseline clinical laboratory visit per protocol section 7.3.7, tables will not be generated. Only listings for abnormal chemistry, hematology, urinalysis, and urine microscopy results for each subject will be provided.

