7.2 LABORATORY PROCEDURES/EVALUATIONS

7.2.1 CLINICAL LABORATORY EVALUATIONS

Samples for clinical laboratory analysis by the central laboratory will be collected by a qualified staff member at the Screening Visit and Months 12, 24, and 36 (EOS)/ET. Refer to the Laboratory Manual for details about collection of specimens. At a minimum, the following tests will be conducted:

- **Chemistry panel:** Albumin, alkaline phosphatase (ALP), alanine aminotransferase (ALT), aspartate aminotransferase (AST), blood urea nitrogen, bicarbonate, calcium, calcium (corrected total), chloride, creatinine, glucose, lactate dehydrogenase (LDH), potassium, sodium, bilirubin (total), and uric acid
- **Hematology:** Hemoglobin, hematocrit, red blood cell (RBC) count, white blood cell (WBC) count with differential, and platelet count
- **Urinalysis:** Clarity, specific gravity, pH, protein, glucose, ketones, nitrite, leukocyte esterase, and occult blood

Urine microscopy will be performed if urinalysis urine protein, leukocyte esterase (WBC esterase), occult blood, or nitrite values are out of range, or if the Investigator deems that the microscopy is clinically warranted.

The Investigator or designee must review the results of each subject's Screening Visit clinical laboratory test results prior to the Day 1 visit. The subject must not be enrolled on Day 1 if any of the Screening Visit results are outside the normal range for the laboratory AND, in the opinion of the Investigator, are indicative of a condition that should prevent the subject from participating.

The results of the clinical laboratory tests will be reported on the laboratory's standard reports. The Investigator must review all laboratory reports in a timely manner, noting "not clinically significant" (NCS) or comment on the clinical significance of any result that is outside the normal range for the laboratory, then date and initial the report. The Investigator must report all laboratory results that are BOTH outside the normal range for the laboratory AND, in the opinion of the Investigator, are clinically significant. If any abnormal, clinically significant laboratory measure is found before study injection on Day 1 that, in the opinion of the Investigator, is not indicative of a condition that should prevent the subject from participating in the study, it should be reported as medical history. Any abnormal, clinically significant AE that is found after Day 1 study injection should be reported as an AE.

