7.3.6 EARLY TERMINATION VISIT

If possible, the following procedures and assessments should be performed within 14 days of subject premature withdrawal or termination.

- Collection of AE and concomitant procedures/therapies/medication data
- Physical examination, including knee examination of both knees
- Weight measurement
- Pregnancy test (urine-based) for WOCBP
- Vital sign measurements (temperature, pulse rate, and blood pressure)

- WOMAC questionnaire
- KOOS questionnaire
- Pain NRS
- SF-12 questionnaire
- PASS questionnaire
- WPAI questionnaire
- 40-meter walk test (at a subset of sites)
- TUG test (at a subset of sites)
- Collection of samples for clinical laboratory tests

Note: PRO measurements (WOMAC, KOOS, pain NRS, SF-12, PASS, WPAI) and functional tests (40-meter walk test and TUG test) do not need to be completed at this visit if they were completed within 2 weeks prior.

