10. CHANGES TO PLANNED ANALYSIS

Change	Protocol Section	Rationale
Analysis of the AEs and clinical laboratory evaluations will not be performed. All available safety data will be listed.	10.4.2	Limited available data. See section 8.1 and 8.2.
Analysis of the efficacy endpoints will not be performed. Available efficacy data will be listed.	10.4.3	Study was terminated early.

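### SAP 8.2 drops laboratory tables because there were no post-baseline laboratory visits, without accounting for the sampling scheduled at Early Termination, and its abnormal-only listing contradicts SAP 10

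*SAP*

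**What the plan says.** SAP 8.2 gives early termination as the background and then its reason for having no tables: "no subjects completed a post baseline clinical laboratory visit per protocol section 7.3.7, tables will not be generated". What remains is stated next: "Only listings for abnormal chemistry, hematology, urinalysis, and urine microscopy results for each subject will be provided".

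The sampling schedule is the same wherever it appears:

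- Protocol 7.2.1 has samples "collected by a qualified staff member at the Screening Visit and Months 12, 24, and 36 (EOS)/ET".
- Protocol 7.3.6, the procedure list for the ET visit, includes "Collection of samples for clinical laboratory tests".
- The Schedule of Events in protocol 7.3.7, the section that SAP 8.2 cites, marks laboratory sampling at Screening, at Months 12 and 24, and in the combined Month 36/ET column.
- SAP 5.4.3 agrees: "Fasting specimens for clinical laboratory analysis were to be collected at Screening Visit and Months 12, 24, and 36 (EOS) or ET".

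On the termination itself, SAP 4 and 5.1.2 say that all active subjects were asked to come for an ET visit, and SAP 4 adds "During the ET visit, only safety data were to be collected". Protocol 8.1 counts clinical laboratory tests among the safety assessments.

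SAP 10 records that adverse events (AEs) and laboratory evaluations will not be analysed, and then says "All available safety data will be listed".

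**The concern.** The reason given in SAP 8.2 does not fit the schedule it cites. The sponsor's decision to stop removed the annual visits, but the same decision triggered the ET visit, which has its own laboratory sample. A reader who follows the cross-reference to 7.3.7 finds a post-baseline sampling point that 8.2 does not account for.

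The listing adds to the difficulty. If only abnormal values are printed, the reader cannot find out from the output whether ET samples were taken at all.

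At stake is the laboratory half of the second safety endpoint, in a study whose primary objective is safety and tolerability. Protocol 10.4.2 also says that safety will be evaluated by laboratory change relative to pre-injection. If nobody reached Month 12, the ET panel is the only scheduled post-injection laboratory measurement a subject could have.

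**Working it through.** No sample-size, power or error-rate figure is involved, so the check sets the passages side by side and works out what the planned output could show.

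**Step 1: which post-baseline samples does early termination explain?**

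| Scheduled post-baseline sample | Source | Explained by stopping early? |
|---|---|---|
| Months 12, 24, 36 | Protocol 7.2.1 and 7.3.7; SAP 5.4.3 | Yes, if no subject reached Month 12 |
| ET | Protocol 7.2.1, 7.3.6 and 7.3.7; SAP 5.4.3 | Not by itself: termination is what prompted the ET visit |

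**Step 2: was laboratory sampling removed from the termination visit?** Nothing in either document says so. SAP 5.1.2 refers ET assessments back to the protocol. The restriction for the sponsor's termination is to safety data, which includes laboratory tests. The note in protocol 7.3.6 that allows some ET assessments to be skipped covers patient-reported outcomes and functional tests only.

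**Step 3: what are the possible states?** Let k be the number of subjects with an ET laboratory panel. The documents give neither k nor the number of ET visits, so k lies between 0 and the number of subjects who attended ET.

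- If k = 0, the factual statement in SAP 8.2 is true but its explanation is incomplete.
- If k is 1 or more, the statement is wrong and k panels are left out of every summary. Each panel holds 16 chemistry + 5 hematology + 9 urinalysis = 30 items, counting the white cell count with differential as one.

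**Step 4: can the planned listing tell these states apart?** For one analyte in one subject:

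| Screening | ET | Printed in an abnormal-only listing | Same as no ET sample? |
|---|---|---|---|
| Normal | Normal | Nothing | Yes |
| Normal | Abnormal | ET value | No |
| Abnormal | Normal | Screening value | Yes |
| Abnormal | Abnormal | Both values | No |

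In 2 of the 4 paired patterns, those with a normal ET value, the output is identical to the output with no ET sample. Changes within the normal range are also invisible, and the number of subjects sampled cannot be counted.

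**Step 5: do SAP 8.2 and SAP 10 agree?** No. A listing of abnormal results is narrower than a listing of all available safety data. This conflict holds whatever k is, because the Screening results alone are enough to produce it.

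**The case against.** The best defence is that SAP 8.2 reports what happened. It was written after termination, as were the statements that only 2 adverse events were reported (SAP 8.1) and that no subject completed the study (SAP 6.1). A schedule says what should be collected, not what was. Subjects were asked to attend ET, and protocol 7.3.6 asks for the ET procedures only where they can be done. Zero ET panels is therefore compatible with everything in the documents. This defence stands, and it rules out some stronger readings.

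- *A reader might infer that post-injection laboratory results exist and are being discarded.* The documents do not show that a single ET panel was drawn.
- *A reader might take SAP 8.3 as proof that ET data were expected.* It keeps change from baseline for weight, and SAP 5.4.2 says "Weight measurements were to be taken at the Screening Visit and at Months 12, 24 and 36 (EOS) or ET", the same visits as for laboratory tests. But 8.3 is one general sentence covering weight and vital signs together. Vital signs are taken at every in-person visit, including Month 3, so the sentence is needed with or without ET weights. It gives a reason to ask and proves nothing.
- *A reader might conclude that a normal-to-abnormal shift cannot be seen.* Usually it can. Protocol 7.2.1 requires Screening results to be reviewed before Day 1. An abnormal ET value with no abnormal Screening entry for that analyte therefore implies a normal Screening value, unless that value was missing.

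The endpoint also has some protection elsewhere. It concerns changes that the investigator judges clinically significant, and protocol 7.2.1 sends such findings after the Day 1 injection to AE reporting. AEs are listed by subject and there are only 2 in all, so at most 2 AE entries could concern laboratory findings. That limits what could have been missed clinically. It does not tell the reader how many subjects were sampled. Without that number, the absence of laboratory AEs cannot be separated from the absence of laboratory tests.

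**Conclusion.** The point holds as an unexplained gap in the rationale together with a contradiction between two SAP sections. The rationale in 8.2 does not account for the ET sampling point in the table it cites, and its abnormal-only listing conflicts with SAP 10. The second finding needs no assumption. The first rests on reading the combined Month 36/ET column as applying to this termination visit, which protocol 7.2.1 and 7.3.6 and SAP 5.4.3 all support.

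The effect on the data cannot be sized beyond the range in the working. At the lower end nothing is lost except a clear statement that part of an endpoint could not be evaluated. At the upper end every scheduled post-injection laboratory panel goes unsummarised, assuming nobody reached Month 12. Because the lower end may well be the truth, the study is descriptive, and clinically significant findings should reach the AE listing, I rate this minor to moderate.

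**What to change.** Revise SAP 8.2 as follows, and align it with 5.4.3 and 10.

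1. List all laboratory results, Screening and any ET, with out-of-range flags, as SAP 10 already promises.
2. State how many subjects attended an ET visit and how many had an ET laboratory sample.
3. If any ET samples exist, correct the stated reason and summarise change from Screening, descriptively, for subjects with both values. A shift table is optional.
4. If none exist, say that the scheduled ET samples were not obtained, give the reason if known, and state that the laboratory part of safety endpoint 2 is not evaluable. Whether a missed sample counts as a deviation should follow the sponsor's existing classification guideline. SAP 6.2 already has a category for laboratory specimens.

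The cost is a few sentences, a longer listing and at most one small table. No new data collection is needed. If there are no ET samples, no table is needed either.
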